1 INTRODUCTION

This Statistical Analysis Plan (SAP) contains a more technical and detailed elaboration of the principal features of the analysis described in the protocol, and includes detailed procedures for executing the statistical analysis of the primary and secondary endpoints and other data.

The SAP is finalized and signed prior to accumulation of a substantial amount of data (open-label study) to ensure lack of bias. For operational efficiency an earlier time is usually targeted and wherever possible, the SAP should be developed in parallel with protocol finalization. If needed, revisions to the approved SAP may be made prior to database hard lock. Revisions will be version controlled.

This statistical analysis is coordinated by the responsible biostatistician of APEB. Any changes from the analyses planned in the SAP will be justified in the Clinical Study Report (CSR).

[figure not shown]
All details of the Pharmacokinetics Analysis Set (PKAS) will be described in a separate analysis plan, and a separate PKAS modeling report will be written.

This SAP is based on protocol version 2.2, dated 15 April 2016 and is an amendment version of SAP versions 1.0 and 2.0.

Prior to database hard lock, a final review of data and TLFs meeting will be held to allow a review of the clinical trial data and to verify the data that will be used for analysis set classification. If required, consequences for the statistical analysis will be discussed and documented. A meeting to determine analysis set classifications may also be held prior to database hard lock.

2 FLOW CHART AND VISIT SCHEDULE

Flow Chart

Study Period: Visit/Week:	Screening Period			Treatment Period					Follow-up Period		Unscheduled Visits	Post study Follow up ^c
	2-6 Weeks ^a			Day 1 ^b	Weekly (Wks 1 to 8) ± 2 days	Every 2 Weeks (Wks 10 to 36) ± 2 days	Every 4 Weeks (Wks 40 to 100) ± 3 days	EOT ^c (Week 104) ± 3 days	EOT + 2 wks ± 3 days	EOS ^c (EOT + 4 wks) ± 3 days		Every 6 months until projected Wk 108
	S1	S2	S3									
Serum Lipid Panel ^l	X			X	Wks 4, 8	Wks 12, 20, 28, 36	Wks 44, 52, 68, 84	X		X	O	
Serum iron, ferritin, TIBC, TSAT ^m	X			X	Wks 4, 8	Wks 12, 20, 28, 36	Wk 44 + every other 8 wks	X		X	O	
HbA1c	X			X		Wk 12, 28, 36	Wks 44, 52, 60, 84	X		X	O	
Vitamin B ₁₂ , folate	X										O	
HIV, HBsAg, anti-HCV Antibody	X										O	
Serum Pregnancy Test (HCG) ⁿ	X					Wks 12, 24, 36	Wks 48, 60, 72, 84, 96	X			O	
high sensitivity C-reactive protein (hs-CRP), hepcidin				X	Wk 4	Wks 12, 20, 36	Wk 52	X		X		
Archival Serum Samples for Biomarkers				X	Wk 4	Wks 12, 20	Wks 52, 76	X		X		
Blood Sample for PK ^o					Wks 2 to 8							
QoL Questionnaires ^p				X	Wk 8	Wks 12, 28, 36	Wks 52, 76	X				
Dialysate ^q					Wks 2 to 8							
Optional genotyping ^r				O								
Study Treatment: roxadustat dispensing OR ESA administration ^s					-----						O	
Dose Adjustment Review ^t					X	X	X				O	
AE and Concomitant Medication Recording	←-----→											
Procedure and non-drug Therapy Recording	←-----→											
Vital status, SAEs, cardiovascular and thromboembolic AEs												X

Footnotes appear on next page

S1/S2/S3=Screening visit 1, 2 and 3; EOT = End of Treatment; EOS = End of Study; Wk(s) = Week(s); X = mandatory test/assessment; O = optional test/assessment. In HD subjects all lab sampling is to be performed prior to or at initiation of the dialysis session.

Note: Instructions for roxadustat-treated subjects moving from Protocol v1.0 to Protocol v2.0 in terms of dosing are provided in Protocol Appendix 12.3.

- ^a Due to the requirement of 4-day separation between the screening Hb values, the screening period will last a minimum of 2 weeks approximately, but is allowed to be a maximum of 6 weeks. Sites are recommended to schedule the three screening visits in the shortest time span possible.
- ^b Randomization and administration of the first dose of study drug (roxadustat or ESA) are to occur on Day 1, which should correspond to a day when the subjects' next dose of epoetin or darbepoetin alfa would have been administered. In HD subjects only, post-dialysis weight and post-dialysis vital signs do not have to be completed prior to randomization and first study drug administration.
- ^c In case of premature treatment discontinuation, the subject will complete the EOT visit and EOS visit. Thereafter subjects who have taken at least one dose of study drug will continue to be followed up at a 6-monthly frequency for vital status, SAEs and cardiovascular and thromboembolic AEs until their projected date of completion of the Follow-up Period (i.e. projected week 108 date) or until consent withdrawn. No additional study visits will be required during the Post study Follow-up.
- ^d Height at first Screening visit only; Weight is post-dialysis weight in HD subjects. For day 1 visit the post-dialysis weight on the third screening visit is to be recorded in the Interactive Response System (IRS) for HD subjects. Weight for PD subjects is the weight measured at site minus the abdominal fluid based on last filling. For drug dispensing purposes (at visits after randomization), weight from the previous dialysis session may be used.
- ^e Targeted physical examination (e.g., respiratory and cardiovascular).
- ^f Blood pressure and heart rate measured singly during the screening period, and in triplicate at all other visits; in HD subjects both pre- and post-dialysis.
- ^g Respiratory rate measured singly during screening period and all other visits; in HD subjects both pre- and post-dialysis.
- ^h Separate Hemoglobin should be collected at all the visits where Complete Blood Count (CBC) is not collected; i.e. Hemoglobin at Weeks 5, 6, 7, 10 until the end of the study. It is recommended that the Hb assessments be performed on the same day of the patient's dialysis schedule throughout the study.
- ⁱ Serum chemistry includes LFTs.
- ^j Renal ultrasound examination can be performed at any time during the screening period. Not required if results of a previous renal ultrasound (or other renal imaging modality such as CT scan or MRI providing a conclusive report on the kidney) within 12 weeks prior to randomization is available and ruling out renal cell carcinoma.
- ^k LFTs to be collected at further visits where Serum Chemistry is not collected.
- ^l Fasting, whenever possible.
- ^m TSAT = [FeSat (Ferro Saturation = % Iron Saturation) measured by central lab and derived from iron and TIBC].
- ⁿ Human chorionic gonadotropin (HCG). To be collected from female subjects of childbearing potential only.
- ^o Only for subjects randomized to roxadustat at 6 time points over 1 to 3 visits. At each PK visit, an additional sample will be collected for albumin and alpha-acidglycoprotein determination.
- ^p Includes Short Form 36 (SF-36), Functional Assessment of Cancer Therapy-Anemia (FACT-An), European Quality of Life 5 Domain 5 Level (EQ-5D 5L) and Patients' Global Impression of Change (PGIC). PGIC will not be performed on Day 1. In HD subjects, the quality of life questionnaires are to be completed by the subject prior to any other assessment or at the latest at the start of dialysis session. It is important that the physician does not discuss the status of the subject prior to completion of the questionnaires. In PD subjects the questionnaires are to be completed prior to any study assessment.

Footnotes continued on next page

- ^q Only for continuous ambulatory peritoneal dialysis (CAPD) subjects randomized to roxadustat. Sample to be withdrawn from the drainage bag after draining complete volume at the site and at the same visit as the PK blood samples (see footnote o).
- ^r Optional assessment and only for subjects randomized to roxadustat. If a separate (optional) informed consent form is signed by the subject, a sample can be collected after randomization, preferably on Day 1.
- ^s Dosing of epoetin alfa and darbepoetin alfa according to approved SmPC (Eprex[®] United Kingdom SmPC; Aranesp[®] European Union SmPC). It is recommended that roxadustat is administered any time after completion of dialysis (if dosing is scheduled on a dialysis day).
- ^t Subjects randomized to roxadustat: dose adjustment review from week 4 onward, and every 4 weeks thereafter until EOT (deviation from the 4-week period is allowed anytime during the study in case of excessive hematopoiesis or Hb \geq 13.0 g/dL). If next dose adjustment interval falls on a non-visit study week, the dose adjustment review should be performed at the next scheduled study visit. ESA dose adjustments should follow the SmPC.

3 STUDY OBJECTIVES AND DESIGN

3.1 Study Objectives

3.1.1 Primary Objective

The primary objective of this study is to evaluate the efficacy of roxadustat compared to ESA (epoetin alfa and darbepoetin alfa) in the maintenance treatment of anemia in End Stage Renal Disease (ESRD) subjects on stable dialysis.

3.1.2 Secondary Objectives

The secondary objectives of this study are to:

- Evaluate the safety of roxadustat compared to ESA (epoetin alfa and darbepoetin alfa) in the maintenance treatment of anemia in ESRD subjects on stable dialysis.
- Evaluate the effects on health-related quality of life (HRQoL) of roxadustat compared to ESA (epoetin alfa and darbepoetin alfa) in the maintenance treatment of anemia in ESRD subjects on stable dialysis.

3.2 Study Design

3.2.1 General

This is a phase 3, multi-center, randomized, open-label, active-controlled study. This study is planned to recruit approximately 750 subjects from approximately 150 study centers, mainly located in Europe.

The study is planned to provide key efficacy and safety data for the approval of roxadustat in the treatment of anemia associated with ESRD on stable dialysis. Study FGCL-4592-064 with similar design is conducted by FibroGen Inc, in study centers across North America, Latin America and Asia Pacific.

3.2.2 Study Population

The study population consists of adult subjects with ESRD who are on stable Hemodialysis (HD) or Peritoneal dialysis (PD) and on stable treatment with epoetin (i.e., epoetin alfa, beta, theta, zeta, delta or omega) or darbepoetin alfa for anemia. Subjects on polyethylene glycol-epoetin beta (Mircera®) are not to be included. Subjects on hemodiafiltration (HDF) are also allowed to participate in the study and will follow the same study procedures and requirements as HD subjects. Prior to randomization a subject must be on the same mode of dialysis for ≥ 4 months and on epoetin or darbepoetin alfa treatment for ≥ 8 weeks with stable average weekly doses (defined as $\leq 30\%$ change) during the last 4 weeks prior to randomization. Anemia is defined as the mean Hb of the three most recent screening measurements ≥ 9.5 g/dL and ≤ 12.0 g/dL with an absolute difference ≤ 1.3 g/dL between the highest and the lowest value. Subjects must be iron replete at baseline; inclusion is permitted if ferritin ≥ 100 ng/mL (≥ 220 pmol/L) and TSAT $\geq 20\%$. Anemia of non-renal origin is to be excluded. Washout periods of at least 4 weeks for any iron-chelating agents, and at least 8 weeks for any RBC

transfusion prior to randomization have been mandated in order to exclude a potential impact of these recent anemia treatments on the assessment of efficacy.

3.2.3 Description of Study

Subjects assigned to the roxadustat treatment arm will receive roxadustat orally as a combination of tablets of different strengths. Subjects assigned to the ESA treatment arm will be administered epoetin alfa if they were on epoetin (i.e., epoetin alfa, beta, theta, zeta, delta or omega) prior to randomization or darbepoetin alfa in case they were on darbepoetin alfa prior to randomization. Study treatment administration is implemented in an open-label manner. Subjects on polyethylene glycol-epoetin beta (Mircera®) are not to be included.

The study will consist of three study periods:

- Screening Period: up to 6 weeks
- Treatment Period: 104 weeks
- Follow-up Period: 4 weeks

During the course of the study, visits and assessments will be performed as defined in the Schedule of Assessments.

Screening Period

During the Screening Period of up to 42 days, eligibility assessments will be performed. Subjects will continue epoetin or darbepoetin alfa treatment per local standard of care.

Subjects meeting all of the inclusion criteria and none of the exclusion criteria will be randomized at Day 1 (baseline), which marks the end of Screening Period and start of the Treatment Period.

Treatment Period

Subjects are randomized to one of two treatment arms as illustrated in [Table 2](#)

Table 2 Treatment Arms, Dosing Frequencies and Patient Numbers

Treatment Arms	Study Treatment	Dosing Frequency	N
1	roxadustat	TIW*	375
2	ESA**	Dosing per SmPC***	375

*TIW = three times weekly; ** ESA = epoetin alfa or darbepoetin alfa

***SmPC = Summary of Product Characteristics

- Treatment arm 1: subjects will be switched from epoetin or darbepoetin alfa treatment to roxadustat treatment (see [Table 3](#) for doses).
- Treatment arm 2: subjects will continue ESA treatment, i.e. epoetin alfa if pre-treated with any epoetin (i.e. epoetin alfa, beta, theta, zeta, delta or omega) and darbepoetin alfa if pre-treated with darbepoetin alfa, at approximately the same average weekly dose the subject was on prior to randomization. It is not allowed to switch from epoetin alfa to darbepoetin alfa or vice versa, during the treatment period.

The initial study drug (roxadustat) dose is based on the dosing scheme shown in [Table 3](#) and is determined by the subject's average prescribed weekly dose of epoetin or darbepoetin alfa within four weeks prior to randomization.

Table 3 Initial Dose of Roxadustat

epoetin* (IU/week)	darbepoetin alfa* (µg/week)	roxadustat (mg/dose) TIW
<8,000	<40	100
8,000 to 16,000	40-80	150**
>16,000	>80	200***

* Average prescribed weekly dose in the last four weeks prior to randomization.

** If the initial dose of 150 mg exceeds the maximum dose of 3.0 mg/kg, then 100 mg is to be used as the starting dose.

*** If the initial dose of 200 mg exceeds the maximum dose of 3.0 mg/kg, then 150 mg is to be used as the starting dose.

The randomization will result in an overall 1:1 ratio of subjects receiving roxadustat administered orally, or epoetin alfa or darbepoetin alfa administered by SC or IV injection.

Randomization to treatment arms will occur through an Interactive Response System (IRS).

Randomization and administration of the first dose of study treatment (roxadustat or ESA) is to occur on Day 1 which should correspond to a day when their next dose of epoetin or darbepoetin alfa would have been administered. The first dose of study treatment should be taken after all study assessments have been completed; in HD subjects only, study assessments should also be performed prior to or at initiation of dialysis (except for post-dialysis weight and post-dialysis vital signs, which should be measured post dialysis).

During the Treatment Period, subjects will attend weekly study visits from Day 1 to Week 8, followed by every other week study visits from Week 10 to 36. Following Week 36, study visits will occur every four weeks until the End of Treatment (EOT).

During the Treatment Period, the aim is to maintain the Hb levels between 10.0 g/dL and 12.0 g/dL. For both treatment arms dose adjustments are to be made based on Hb values using HemoCue®, a point-of-care device.

All subjects receiving roxadustat will initiate and continue roxadustat dosing at a dosing frequency of TIW throughout the entire period and dose adjustment is to follow pre-specified dose adjustment rules (see protocol, Section 5.1.2.1, Table 4). Intake should occur at approximately the same time of day and, if possible, dosing days should remain consistent throughout the study. For HD subjects it is recommended that roxadustat is administered any time after completion of dialysis if dosing is scheduled on a dialysis day to avoid potential bias on certain study assessments. Specific rules apply on the dialysis day(s) at which PK sampling is scheduled (see protocol, Section 5.6).

Subjects will receive study treatment (roxadustat or ESA) for 104 weeks.

Follow-up Period

After the end of the Treatment Period subjects will proceed to the 4-week Follow-up Period. The choice of anemia treatment during the follow-up period is at the discretion of the investigator and according to local standards.

Post Study Follow-up (*only for subjects prematurely discontinued from treatment*)

Subjects who have prematurely discontinued study treatment will complete the EOT and EOS visits. Thereafter, these subjects who have taken at least one dose of study treatment, will continue to be followed up at a 6-monthly frequency for vital status, SAEs and cardiovascular and thromboembolic AEs until their projected date of completion of the Follow-up Period (i.e. projected week 108) or until consent withdrawn. Data collection during this Post study Follow-up occur through phone calls or information collected from source data of subjects' regular, non-study, visits to the clinic. No additional study visits will be required from these subjects during the Post study Follow-up. The last Post study Follow-up data collection should occur around the projected week 108.

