#### 2.2.1.3 Description of Study

Subjects assigned to the roxadustat treatment arm will receive roxadustat orally as a combination of tablets of different strengths. Subjects assigned to the ESA treatment arm will be administered epoetin alfa if they were on epoetin (i.e. epoetin alfa, beta, theta, zeta, delta or omega) prior to randomization or darbepoetin alfa in case they were on darbepoetin alfa prior to randomization. Study treatment administration is implemented in an open-label manner. Subjects on polyethylene glycol-epoetin beta (Mircera®) are not to be included.

The study will consist of 3 study periods:

- Screening Period: up to 6 weeks
- Treatment Period: For all subjects in the study the minimum treatment duration will be 52 weeks and the maximum treatment duration will be 104 weeks. The study end date will be declared when the targeted number of MACE\* and MACE+\*\* events have been reported across the roxadustat phase 3 development program and consequently the treatment will end for all subjects who have completed 52 weeks at that point. Subjects

who have not completed 52 weeks when the target has been declared will continue until they reach 52 weeks and at that point their treatment will end.

- Follow-up Period: 4 weeks

- \* MACE: Major cardiovascular adverse events: myocardial infarction, stroke, death from all causes

- \*\* MACE+: Myocardial infarction, stroke, death from all causes, chronic heart failure requiring hospitalization, unstable angina requiring hospitalization

During the course of the study, visits and assessments will be performed as defined in the Schedule of Assessments [Table 1].

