## Maximum dose for roxadustat

The maximum allowed roxadustat dose in this study is set at 3.0 mg/kg (based on postdialysis weight in HD subjects and weight minus abdominal fluid based on last filling in PD subjects) or 400 mg per administration, whichever is lower. The highest dose tested in healthy subjects is 5 mg/kg single dose and 3.75 mg/kg TIW. The doses were safe and well tolerated with transient dose dependent heart rate increases observed. No maximum tolerated dose was reached in the clinical development of roxadustat based on the observed pharmaco-dynamic response (plasma EPO levels) and the predicted relation between EPO levels and Hb response; therefore exploration of higher doses was not deemed necessary. Plasma EPO levels increased in a supra-linear manner with increasing roxadustat doses. It is expected that the majority of the subjects will show adequate Hb response at substantially lower doses than the maximum allowed dose.

The treatment period of 104 weeks will provide sufficient data on the efficacy and safety of long term treatment of anemia with roxadustat in ESRD subjects on stable dialysis.

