## 5.1 Dosing and Administration of Study Drugs and Other Medication

### 5.1.1 Dose/Dose Regimen and Administration Period

Following the screening period, eligible subjects who are randomized will enter the treatment period (day 1). Treatment will be given in an open label manner.

- Subjects will be randomized via IRS to receive roxadustat or ESA (epoetin alfa or darbepoetin alfa). Randomization and administration of the first dose of study treatment (roxadustat or ESA) are to occur on day 1, which should correspond to a day when the subjects' next dose of epoetin or darbepoetin alfa would have been administered. The first dose of study treatment should be taken after all study assessments have been completed; in HD subjects only, study assessments should also be performed prior to or at initiation of dialysis (except for postdialysis weight and postdialysis vital signs, which should be measured post dialysis).
- All subjects will be treated for a minimum of 52 and a maximum of 104 weeks.

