12	Change from BL to the average value of weeks 12 to 28 (SF-36 Physical Component Score (PCS), Anemia Subscale (“Additional Concerns”) of Functional Assessment of Cancer Therapy (FACT-An) Score, Total FACT-An Score, EQ-5D 5L VAS Score).
13	Patient Global Impression of Change (PGIC).
	Hepcidin, Iron status, HbA1c
14	Changes from BL to each study visit (when measured) in Serum hepcidin, Serum ferritin, TSAT and HbA1c level.

6.1.3.1 Hb response regardless of use of rescue therapy.

Hb response is defined as the mean Hb during weeks 28 to 36 within the target range of 10.0 to 12.0 g/dL. The same rules as defined in Section 6.1.2.1 apply for this endpoint, except that is defined regardless of use of rescue therapy (values in the rescue period will be used too).

Additional endpoints to be used are mean Hb \geq 10.0 g/dL over weeks 28 to 36 and Hb response (defined as mean Hb values between 10.0 to 12.0 g/dL and also defined as mean Hb values \geq 10.0 g/dL) during weeks 28 to 52.

6.1.3.2 Hb change from BL to each post-dosing time point.

All scheduled and unscheduled hemoglobin values that belong to each window will be taken into account using one value per analysis window, as defined in Table 32 and Section 7.11.4

Baseline Hb is defined in Section 6.1.1.1

At each visit, Hb will also be categorized into the following categories: <10 g/dL, 10-12 g/dL and > 12 g/dL.

6.1.3.3 Hb level averaged over weeks 28 to 36, 44 to 52, and 96 to 104 without use of rescue therapy within 6 weeks prior to and during these 8-week evaluation periods.

All scheduled and unscheduled hemoglobin values that belong to each period will be taken into account for calculating the average using the analysis windows (defined in Table 32 Section 7.11.4).

In addition, the averages over weeks 28-36, 44-52 and 96-104 will be categorized into the following categories:

- <10 g/dL,
- \geq 10 g/dL,
- 10-12 g/dL,
- >12 g/dL.

In case a subject does not have any available Hb value within this evaluation period, or in case a subject requires rescue therapy within 6 weeks prior to and during this 8-week evaluation period, refer to Section 7.11.1 for imputation rules.

6.1.3.4 Hb change from BL to the average Hb value of weeks 28 to 36, 44 to 52, and 96 to 104 regardless of the use of rescue therapy.

The same rules as defined in Section 6.1.1 apply for these periods except that it is regardless of rescue therapy.

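### SAP v3.0 still assumes 104 weeks of treatment for everyone, so its weeks 96–104 Hb category table has no rule for subjects whose treatment ended as planned before that window

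*SAP*

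**What the plan says.** **Protocol v3.0 (30 May 2017).** Section 2.2.1.3 states: "For all subjects in the study the minimum treatment duration will be 52 weeks and the maximum treatment duration will be 104 weeks". Section 5.1.1 agrees: "All subjects will be treated for a minimum of 52 and a maximum of 104 weeks". Treatment stops for everyone past week 52 once the program's MACE and MACE+ target is declared, and subjects not yet at week 52 continue to week 52. Section 2.2.2, under the maximum dose, still reads "The treatment period of 104 weeks will provide sufficient data on the efficacy and safety of long term treatment".

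**SAP v3.0 (10 September 2018).** Section 1 states: "This SAP is based on protocol version 2.2, dated 15 April 2016". Section 3.2.3 gives "Treatment Period: 104 weeks" and repeats that "Subjects will receive study treatment (roxadustat or ESA) for 104 weeks". The key terms, the flow chart and 3.2.3 run post-study follow-up to projected week 108. Tables 32 to 34 each have two rows for the EOT visit: one for completers, tied to week 104, and one for premature discontinuations.

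**Weeks 96–104 Hb average.** SAP 6.1.3.3 averages Hb over this window and sorts the average into <10, ≥10, 10–12 and >12 g/dL. It then says "In case a subject does not have any available Hb value within this evaluation period", or if rescue therapy was needed, the reader should go to 7.11.1 for imputation. SAP 7.4.3.3 reports the number and proportion of subjects in each category.

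**The concern.** Under the current protocol, a subject can finish treatment exactly as planned and never be due for a visit at week 96. The SAP does not recognise that case. Its only instruction for a subject without Hb in the window is the cross-reference to 7.11.1, which was written for a design in which such a value is missing.

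At stake is the meaning of one reported table. If planned ends are filled with an average reaching back to Day 1, the weeks 96–104 categories would partly describe the first year, including the pre-dose value and the weekly visits of the first 8 weeks. A table read as evidence of two-year Hb maintenance would then rest in part on earlier data, and its denominator would include subjects who were never due to be observed there.

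**Working it through.** The plan states no expected number of subjects at weeks 96–104, so it has no figure of its own to reproduce. The check rests on the text and on day counts.

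**1. Which design the SAP describes.** SAP v3.0 is dated after protocol v3.0 but names protocol v2.2 as its base. It plans no interim analysis, which agrees with protocol v3.0, yet it keeps the fixed 104 weeks and the week 108 follow-up. None of the ten changes listed for SAP v3.0 concerns treatment duration.

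**2. When the window opens.** Table 32 sets the target day at 7 × week + 1, with 14 days allowed before the target for weeks 40 to 100.
- Week 96 target: 7 × 96 + 1 = day 673. The window opens on day 673 − 14 = 659, and (659 − 1)/7 = week 94.
- Earliest planned end: 7 × 52 + 1 = day 365.
- Gap: 659 − 365 = 294 days, or 42 weeks.

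A subject whose treatment ends by design before about week 94 has no on-treatment Hb in the window.

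**3. Which rule in 7.11.1 could supply a category.**

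| Rule in 7.11.1 | Written for | One value per subject? |
|---|---|---|
| MMRM | continuous endpoints | no, implicit imputation only |
| ANCOVA with MI | continuous endpoints | no, many imputed data sets |
| Pattern mixture models | continuous endpoints | no, multiple imputation |
| Mean of values from Day 1, carried forward | response variables | yes |

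Only the last row gives a single value that can be placed in a category. The 10–12 g/dL category also uses the same range as the SAP's Hb response, which makes this reading a natural one for a programmer. Section 6.1.3.3 does not say which rule it means.

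**4. What that mean would contain.** Count Hb at Day 1 and at every scheduled visit (flow chart and its footnote on Hb), with no missed or unscheduled visits.
- Planned end at week 52: Day 1 (1) + weeks 1–8 (8) + weeks 10–36 every 2 weeks (14) + weeks 40–52 every 4 weeks (4) = 27 values.
- Before week 28: 1 + 8 + 9 (weeks 10–26) = 18, and 18/27 = 67%.
- Planned end at week 92: 1 + 8 + 14 + 14 = 37 values, of which 18/37 = 49% are from before week 28.

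**5. How many subjects.** The documents give neither the accrual pattern nor the date on which the event target is declared. The possible share with a planned end before day 659 runs from 0 to 100%. As an illustration only, if planned durations were uniform from week 52 to week 104 (day 729), it would be (659 − 365)/(729 − 365) = 294/364 = 81%.

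**6. What lies outside the problem.** The EU and US primary windows are weeks 28–36 and 28–52, and every key secondary endpoint ends by week 36. All fall within the 52-week minimum, so sample size and power do not change.

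**The case against.** The strongest reply is that the SAP never prescribes a Day 1 average at weeks 96–104. Section 7.11.1 confines that rule to response variables, and Hb response is defined only for weeks 28–36 and 28–52. The continuous weeks 96–104 endpoints in 7.4.3.3 and 7.4.3.4 follow the MMRM of 7.4.1.1.1, which assigns no subject such an average. A planned end triggered by a program-wide event count is administrative censoring, for which missing at random is plausible. All of this stands. It leaves open what 7.11.1 requires for the categories in 6.1.3.3.

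A reader might also infer that late drift in Hb would be hidden altogether. The documents do not support that. Hb by visit, the MMRM change to weeks 96–104, per-subject proportions of Hb values in several late windows, and the percentage of time in each Hb range all show late Hb without the Day 1 mean.

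Nor does a conflict with 6.1.3.5 follow. Its no-imputation sentence sits under percentage of time, and a proportion of a subject's values is a different quantity from the category of that subject's mean.

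Finally, the missing EOT row misplaces no data, because values are windowed by actual day. A planned end at week 70 (day 491) falls in the ordinary Week 40–100 windows. SAP 6.5.2 already censors subjects who completed treatment at the EOT visit, and exposure is tabulated in bands that include 52–78, 78–104 and 104 weeks or more. It is therefore not shown that drop-outs and planned ends would be mixed. The text only fails to say that a planned end before week 104 is completion, while 3.2.3 gives the treatment period as 104 weeks.

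**Conclusion.** The point holds in a narrow form. SAP v3.0 describes a treatment duration that the current protocol no longer has, and its weeks 96–104 category table lacks a rule for subjects whose treatment ended by design before about week 94. On a plausible reading of 7.11.1, those subjects would receive a category built from earlier data: 18 of 27 scheduled values from before week 28 for a planned end at week 52, and 18 of 37 for one at week 92. These counts assume Hb at every scheduled visit and no unscheduled values.

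It would go too far to say that the SAP instructs this imputation, or that a known fraction of the table would be imputed. The first is an ambiguity in a cross-reference. The second needs accrual and declaration dates that the documents do not give. The effect is confined to a descriptive summary of an additional secondary endpoint. The weeks 96–104 MMRM analyses and all primary and key secondary endpoints are untouched.

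**What to change.** 1. Align SAP 3.2.3, the week 108 references and the EOT rows of Tables 32 to 34 with protocol v3.0, adding a row for completers before week 104 that maps to the actual visit window.
2. State that an end of treatment due to the declared study end counts as completion and is censored at EOT in the time-to-discontinuation analysis.
3. For the weeks 96–104 category table, make no imputation after a planned end. Report observed cases and show by arm the number whose planned treatment reached the window. The weeks 72–80 average that 7.4.3.3 adds to the same table needs the same rule.
4. Leave the MMRM analyses on all subjects. Restricting them to subjects whose planned treatment reached the window would discard valid data.
5. Reconcile the 104-week statement in protocol 2.2.2 with protocol 2.2.1.3.

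The cost is SAP wording and some programming, plus one correction to the protocol text. The downside is smaller numbers in the weeks 96–104 category table.
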